3.3 Number of Subjects

The study will enroll up to approximately 90 to 100 subjects. It is estimated that approximately 30 subjects will be treated in Phase 1 and approximately 60 to 70 subjects will be treated in the Phase 2 portion of the study.

3.4 Schedules of Evaluations

Table 4: Phase 1: Schedule of Evaluations

Week ⁴	Screen n ⁵	Treatment Period (Cycle ¹)												Follow-up	
		1		2		3		4		5		6		7	
		1	2	3	5	8	1	1	1	1	2	23	2	29/ EO T	32
Informed consent	X														
Inclusion/Exclusion	X														
Demog/med hx ⁶	X														
Adverse events															X ⁷
Concomitant Meds															X ⁸
ECOG	X	X		X	X	X				X			X	X	X
CBC with diff	X	X ₉	X	X	X	X	X			X			X	X	X
Coagulation ¹⁰	X	X ₉		X	X	X				X			X	X	X
Chemistry profile	X	X ₉	X	X	X	X	X			X			X	X	X
Thyroid functions	X		X		X	X	X			X			X	X	X
CH50/C3/C4	X			X	X	X				X			X	X	X
Urinalysis	X				X					X					X
Vital signs ¹¹	X	X	X	X	X	X	X			X			X	X	X
ECG	X		X ₁₂				X ₁₂								X
Directed physical ¹³	X	X			X	X	X			X			X	X	X
Pregnancy test	X														X
Tumor biopsies/biomarkers ¹⁴	X	X ₁₅	X ₁₆		X		X ₁₆						X ₁₆		
Blood biomarkers		X ₁₅	X ₁₅		X ₁₇	X ¹ ₇							X ¹⁷		
Radiology	X					X ₁₈				X ₁₈			X ¹⁸		X ¹⁹
Response ²⁰						X ₁₈				X ₁₈			X ¹⁸		X ¹⁹
PRO ²¹		X				X				X			X		X ¹⁹
IMO-2125 dosing		X	X	X	X	X	X			X			X	X	

Week ⁴	Screening ⁵	Treatment Period (Cycle ¹)												Follow-up	
		1		2	3	4		5		6		7		Safety ²	Ongoing ³ (every 3 months)
		1	2	3	5	8	1	1	1	2	23	2	29/EO T	32	
Ipilimumab dosing			X		X	X	X								
Pembrolizumab dosing			X		X	X	X	X	X	X	X	X	X	X ²²	X ²²
PK testing ²³		X	X	X	X	X	X		X ²⁴			X ²⁴	X ²⁴	X ²⁴	
Immunogenicity ²⁵		X			X		X		X			X	X	X	X ²⁶

Abbreviations: AE=adverse event; aPTT=activated partial thromboplastin time; C3=complement component 3; C4=complement component 4; CBC=complete blood count; CH50=total hemolytic complement activity 50; CR=complete response; CT=computed tomography; Demogr=Demographic; diff=differential; ECG=electrocardiogram; ECOG=Eastern Cooperative Oncology Group; EOT= End of Treatment; hx=history; INR=international normalized ratio; irRC=immune-related response criteria; med=medical; PK=pharmacokinetic; PR=partial response; PRO = patient reported outcomes; PT=prothrombin time

¹ Please note, the number of weeks per cycle varies. Cycle 1 is 4 weeks in length to account for an IMO-2125 priming dose. Cycles 2, 3, and 4 are 3 weeks in length, and Cycles 5, 6, and 7 are included as maintenance dosing and are 6 weeks in length.

² The Safety Follow-up Visit should be 21 days following the last dose of IMO-2125 (\pm 5 days).

³ Includes ongoing follow-up every 3 months until documented disease progression, next melanoma treatment, withdrawal of consent, death, or Sponsor notification that follow-up is no longer required.

⁴ All assessments and IMO-2125 dosing will occur within a \pm 2-day window. Ipilimumab and pembrolizumab will be dosed per their respective labels.

⁵ All Screening tests and assessments must be performed within 21 days of the start of Week 1 of Cycle 1, unless otherwise noted. All patients who sign an informed consent and are screened and qualify for the study will be considered enrolled.

⁶ Including melanoma history and prior melanoma treatment history.

⁷ Grade ≤ 2 AEs do not need to be reported.

⁸ Only concomitant medications for the treatment of Grade ≥ 3 AEs will be captured.

⁹ CBC with differential should be done 24 to 48 hours after the IMO-2125 injection, to coincide with the post-injection biopsy. Chemistry profile and coagulation tests do not have to be conducted if Screening tests were conducted within 7 days of the Cycle 1 Week 1 Visit.

¹⁰ PT, aPTT, INR.

¹¹ Blood pressure, heart rate, respiratory rate, and temperature.

¹² Week 2 ECG pre-dose and at 2 hours post-IMO-2125 administration. Week 11 ECG at 2 hours post-IMO-2125 administration.

¹³ Including assessment of melanoma lesions.

¹⁴ Biopsy of the tumor to be injected with IMO-2125 and biopsy of a tumor that will not be injected. See Section 13.2 of the protocol and the Laboratory Manual for details on the collection of biopsies and analyses of biomarkers.

¹⁵ Biopsy of the injected tumor should occur within 24 to 48 hours after injection (no more than 48 hours). Collection of blood for biomarkers should occur on Day 1 pre-IMO-2125 administration, 4 hours after IMO-2125

administration, and 24 to 48 hours after injection (coinciding with the 24-hour PK sample). At Week 2, collect before ipilimumab or pembrolizumab dosing.

¹⁶ Optional biopsy.

¹⁷ At Weeks 5 and 8, collect pre-ipilimumab or pre-pembrolizumab dosing and post-IMO-2125 dosing. At Week 29/EOT collect pre-pembrolizumab dosing (for subjects in that arm who have pembrolizumab continued) and post-IMO-2125 dosing. If no ipilimumab or pembrolizumab is given at the specified visit(s) collect the samples pre- and post-IMO-2125 dosing. If no IMO-2125 if given, then collect pre- and post- ipilimumab or pembrolizumab.

¹⁸ Radiologic assessment and Investigator assessment of response at Week 8, Week 17, and Week 29 may be conducted within a ± 7 -day window.

¹⁹ At least every 3 months until progression, start of next melanoma treatment, withdrawal of consent, death, or Sponsor notification that follow up is no longer required.

²⁰ In Phase 1, response assessed using irRC and RECIST v 1.1. Best response to first subsequent treatment should also be captured. Confirmatory scans for CR, PR, and progressive disease should be performed ≥ 4 weeks after the date the response was first documented.

²¹ To minimize bias in the PRO data, the PRO assessments should be completed before study drug administration and AE assessments.

²² For patients assigned to the IMO-2125 + pembrolizumab treatment arm, continued pembrolizumab dosing per the approved product label is permitted at the discretion of the Investigator.

²³ PK: blood sampling for analysis of plasma concentrations of IMO-2125 and serum concentrations of ipilimumab, and pembrolizumab (See Table 3 of the protocol for specific collection times).

²⁴ For patients who continue pembrolizumab treatment, pembrolizumab pre-dose PK samples should be collected before dosing at all visits. A post-dose pembrolizumab PK sample should be collected 30 minutes after initiation of pembrolizumab infusion at Week 23. Pharmacokinetic samples at Week 33 are optional.

²⁵ Immunogenicity: blood sampling for analysis of antibodies to IMO-2125, ipilimumab, and pembrolizumab will be performed prior to any dosing at that visit.

²⁶ For patients in Ongoing Follow-up (i.e., those discontinued from study treatment before progression or new anticancer treatment), the immunogenicity samples are required at the scheduled visits. For patients in survival follow-up (i.e., after progressive disease or start of new anti-cancer treatment), immunogenicity assessments are optional (e.g., if a patient comes to the investigator site for a Survival Follow-up Visit rather than the usual telephone contact).

Table 5: Phase 2 Schedule of Evaluations

Week ⁴	Screen ⁵	Treatment Period (Cycle ¹)												Follow-up	
		1		2	3	4			5		6		7	Safety ²	Ongoing ³ (every 3 months)
		1	2	3	5	8	11	13	14	17	20	23	26	29/ EOT	32
Informed consent	X														
Inclusion/Exclusion	X														
Demog/med hx ⁶	X														
Adverse events															X ⁷
Concomitant Meds															X ⁸
ECOG	X	X			X	X	X			X		X		X	X
CBC with diff	X	X ₉	X	X	X	X	X			X		X		X	X
Coagulation ¹⁰	X	X ₉			X	X	X			X		X		X	X
Chemistry profile	X	X ₉	X	X	X	X	X			X		X		X	X
Thyroid functions	X		X		X	X	X			X		X		X	X
CH50/C3/C4	X				X	X	X			X		X		X	X
Urinalysis	X					X				X					X
Vital signs ¹¹	X	X	X	X	X	X	X			X		X		X	X
ECG	X		X ₁₂				X ¹²								X
Directed physical ¹³	X	X			X	X	X			X		X		X	X
Pregnancy test	X														X
Tumor biopsies/biomarkers ¹⁴	X	X ₁₅	X			X		X				X			
Blood biomarkers		X ₁₆	X ₁₆			X ¹⁶									
Radiology	X					X ₁₇			X ₁₇				X ¹⁷		X ¹⁸
Response ¹⁹						X ₁₇			X ₁₇				X ¹⁷		X ¹⁸
PRO ²⁰		X				X			X				X		X ¹⁸
IMO-2125 dosing		X	X	X	X	X	X		X		X		X		
Ipilimumab dosing		X		X	X	X									
Pembrolizumab dosing			X		X	X	X		X	X	X	X	X	X ²¹	X ²¹
PK testing ²²		X	X	X	X	X	X		X ₂₃		X ₂₃		X ²³	X ²³	
Immunogenicity ²⁴		X			X		X		X		X		X	X	X ²⁵

Abbreviations: AE=adverse event; aPTT=activated partial thromboplastin time; C3=complement component 3; C4=complement component 4; CBC=complete blood count; CH50=total hemolytic complement activity 50; CR=complete response; CT=computed tomography; Demogr=Demographic; diff=differential; ECG=electrocardiogram; ECOG=Eastern Cooperative Oncology Group; EOT= End of Treatment; hx=history; INR=international normalized ratio; irRC=immune-related response criteria; med=medical; PK=pharmacokinetic; PR=partial response; PRO = patient reported outcomes; PT=prothrombin time

¹ Please note, the number of weeks per cycle varies. Cycle 1 is 4 weeks in length to account for an IMO-2125 priming dose. Cycles 2, 3, and 4 are 3 weeks in length, and Cycles 5, 6, and 7 are included as maintenance dosing and are 6 weeks in length.

² The Safety Follow-up Visit should be 21 days following the last dose of IMO-2125 (\pm 5 days).

³ Includes ongoing follow-up every 3 months until documented disease progression, next melanoma treatment, withdrawal of consent, death, or Sponsor notification that follow-up is no longer required.

⁴ All assessments and IMO-2125 dosing will occur within a \pm 2-day window. Ipilimumab and pembrolizumab will be dosed per their respective labels.

⁵ All Screening tests and assessments must be performed within 21 days of the start of Week 1 of Cycle 1, unless otherwise noted. All patients who sign an informed consent and are screened and qualify for the study will be considered enrolled.

⁶ Including melanoma history and prior melanoma treatment history.

⁷ Grade \leq 2 AEs do not need to be reported.

⁸ Only concomitant medications for the treatment of Grade \geq 3 AEs will be captured.

⁹ CBC with differential should be done 24 to 48 hours after the IMO-2125 injection, to coincide with the post-injection biopsy (if the biopsy is conducted). Chemistry profile and coagulation tests do not have to be conducted if Screening tests were conducted within 7 days of the Cycle 1 Week 1 Visit.

¹⁰PT, aPTT, INR.

¹¹ Blood pressure, heart rate, respiratory rate, and temperature.

¹² Week 2 ECG pre-dose and at 2 hours post-IMO-2125 administration. Week 11 ECG at 2 hours post-IMO-2125 administration.

¹³ Including assessment of melanoma lesions.

¹⁴ In Phase 2, all tumor biopsies are optional. See Section 13.2 of the protocol and the Laboratory Manual for details on the collection of biopsies and analyses of biomarkers.

¹⁵ Biopsy of the injected tumor should occur within 24 to 48 hours after injection (no more than 48 hours).

¹⁶ In Phase 2, blood biomarker samples will be collected from at least 20 patients treated at the IMO-2125 RP2D after which the Sponsor will determine if additional samples are needed. The blood biomarker samples will be collected on Day 1 before IMO-2125 administration, 4 hours after IMO-2125 administration, and 24 to 48 hours (coinciding with the 24-hour PK sample) after the injection. At Week 2 and Cycle 3 Week 8, collect before ipilimumab or pembrolizumab dosing.

¹⁷ Radiologic assessment and Investigator assessment of response at Week 8, Week 17, and Week 29 may be conducted within a \pm 7-day window.

¹⁸ At least every 3 months until progression, start of next melanoma treatment, withdrawal of consent, death, or Sponsor notification that follow up is no longer required.

¹⁹ In Phase 2, response assessed using irRECIST and RECIST v 1.1. Best response to first subsequent treatment should also be captured. Confirmatory scans for CR, PR, and progressive disease should be performed \geq 4 weeks after the date the response was first documented.

²⁰ To minimize bias in the PRO data, the PRO assessments should be completed before study drug administration and AE assessments.

²¹ For patients assigned to the IMO-2125 + pembrolizumab treatment arm, continued pembrolizumab dosing per the approved product label is permitted at the discretion of the Investigator.

²² PK: blood sampling for analysis of plasma concentrations of IMO-2125 and serum concentrations of ipilimumab, and pembrolizumab (See **Error! Reference source not found.**Table 3 of the protocol for specific collection

times). For each combination in Phase 2, the collection of plasma concentration samples will be done on at least 20 patients treated at the IMO-2125 RP2D after which the Sponsor will determine if additional samples are needed.

²³ For patients who continue pembrolizumab treatment, pembrolizumab pre-dose PK samples should be collected before dosing at all visits. A post-dose pembrolizumab PK sample should be collected 30 minutes after initiation of pembrolizumab infusion at Week 23. Pharmacokinetic samples at Week 33 are optional.

²⁴ Immunogenicity: blood sampling for analysis of antibodies to IMO-2125, ipilimumab, and pembrolizumab will be performed prior to any dosing at that visit.

²⁵ For patients in Ongoing Follow-up (i.e., those discontinued from study treatment before progression or new anticancer treatment), the immunogenicity samples are required at the scheduled visits. For patients in survival follow-up (i.e., after progressive disease or start of new anti-cancer treatment), immunogenicity assessments are optional (e.g., if a patient comes to the investigator site for a Survival Follow-up Visit rather than the usual telephone contact).

Table 5.1: Schedule of PK Blood Sampling for IMO-2125, Ipilimumab, and Pembrolizumab

	Cycle 1			Cycle 2	Cycle 3	Cycle 4			Cycle 5		Cycle 6		Cycle 7	Safety Follow -Up ¹
	Week 1	Week 2	Week 3	Week 5	Week 8	Week 11	Week 14	Week 17	Week 20	Week 23	Week 26	Week 29/ EOT	Week 32	
IMO-2125														
Pre-dose	X	X	X	X	X	X						X		
Post-dose														X ²
30 m (± 5 m)	X					X						X		
1 h (± 10 m)	X					X						X		
1.5 h (± 10 m)	X					X						X		
3 h (± 15 m)	X					X						X		
Ipilimumab														
Pre-dose		X		X	X	X			X ³		X ³			
Post-dose														X ²
90 m after start of infusion (± 5 m)		X				X								
Pembrolizumab														
Pre-dose		X		X	X	X	X	X	X	X	X	X	X	X ²
Post-dose														
30 m after start of infusion (± 5 m)		X				X				X				X ²

Abbreviations: EOT=End of Treatment; h=hour; m=minute; PK=pharmacokinetic

¹ Collection of PK samples at the Safety Follow-up Visit is optional.

² IMO-2125 (plasma samples) and ipilimumab (serum) PK samples may be collected at any time during the Safety Follow-up Visit. Optional pre- and post-dose pembrolizumab serum PK samples are collected for those patients continuing pembrolizumab treatment at this visit. If pembrolizumab treatment was stopped, a sample may be collected at any time during the visit.

³ Pre-IMO-2125 dose.

4. DETERMINATION OF SAMPLE SIZE

The primary objective of Phase 2 is to assess the preliminary clinical activity, defined as the investigator assessed RECIST v1.1 ORR, of IMO-2125 in combination with ipilimumab or of IMO-2125 in combination with pembrolizumab in subjects with progression on or following PD-(L)1 therapy for metastatic melanoma. Given that two primary hypotheses are being tested (regarding the ORR of IMO-2125 and ipilimumab and the ORR of IMO-2125 and

pembrolizumab), a Bonferroni correction has been applied to the alpha to control for Type I error for the trial.

Assuming the immune-related ORR for subjects who receive ipilimumab alone is at most 11% (the historical response rate in subjects who are PD-1 inhibitor naïve), and a target immune-related ORR of 35% for subjects who receive the IMO-2125 ipilimumab combination treatment, a sample size of 21 subjects would achieve 77% power to detect a 24% difference in response rates using a one-sided significance level of 2.5%.

The IMO-2125 + ipilimumab treatment arm will use a two-stage design with a targeted Type I error rate of 0.025 to test the null response rate of 0.11 against the alternative of at least 35%. With this method, 10 subjects will be treated and monitored for an RECIST v1.1 response in the first stage. For this arm, if 2 or more subjects have an RECIST v1.1 response in Stage 1, then the treatment arm will continue to Stage 2, in which 11 more subjects will be treated. If at least 6 of the 21 total subjects have an RECIST v1.1 response, then the null hypothesis H_0 will be rejected in favor of the alternative H_a . In this treatment arm, this design has statistical power of 77%, an expected sample size of 13.33, and a probability of stopping at the end of the first stage of 69.7% if the response proportion is ≤ 0.11 .

The IMO-2125 + pembrolizumab treatment arm will use a two-stage design with a targeted Type I error rate of 0.025 to test the null response rate against the alternative of at least 35%. If at least 1 subject has an RECIST v1.1 response in Stage 1, then the treatment arm will continue to Stage 2 and treat 11 additional subjects. If at least 4 of the 21 total subjects have an RECIST v1.1 response, then the null hypothesis H_0 will be rejected in favor of the alternative H_a . In this treatment arm, this design has statistical power of 96%, an expected sample size of 14.41, and a probability of stopping at the end of the first stage of 60% if the response proportion is ≤ 0.05 .

5. GENERAL ANALYSIS CONSIDERATIONS

The statistical analyses will be reported using summary tables, listings, and figures (TLFs). The International Conference on Harmonisation (ICH) numbering convention will be used for all TLFs. Unless otherwise noted, all statistical testing will be one-sided and will be performed at the 0.025 significance level. Tests will be declared statistically significant if the calculated p-value is less than or equal to the significance level of the test, usually 0.025. Continuous variables will be summarized with means, standard deviations, medians, minimums, and maximums. For continuous variables, descriptive statistics will include the number of non-missing values, mean, standard deviation, median, 25th and 75th percentile, minimum, maximum, and 95% confidence intervals (CIs) as appropriate. All durations will be reported in months.

For categorical variables, descriptive statistics will include counts and percentages per category. Statistics describing time-to-event variables will use the Kaplan-Meier method. Individual subject data obtained will be presented by subject in data listings. Dose group will be used to identify the dose and study treatment cohort in the Phase 1 portion of the trial; treatment arm will identify the treatment arm in the Phase 2 portion of the study. All analysis will be done using these descriptors.

The analyses described in this plan are considered *a priori*, in that they have been defined prior to database lock. All analyses and tabulations will be performed using SAS® Version 9.2 or higher. Tables and listings will be presented in RTF format. All SAS® programs will be validated by an independent programmer. In addition, all program output will undergo a senior level statistical review. The validation process will be used to confirm that statistically valid methods have been implemented and that all data manipulations and calculations are accurate. Checks will be made to ensure accuracy, consistency with this plan, consistency within tables, and consistency between tables and corresponding data listings. Upon completion of validation and quality review procedures, all documentation will be collected and filed by the project statistician or designee.

6. ANALYSIS POPULATIONS

The following analysis population will be used for safety analyses:

- Safety Population: all patients who received at least one dose of IMO-2125.

The following analysis population will be used only for Cohort Review Committee meetings to determine if the dose may be escalated.

- DLT Evaluable Population: all patients in the Safety Population who continue participation in the study for the entire DLT evaluation period, or who discontinue prematurely due to a DLT.

The following analysis populations will be used for efficacy analyses:

- Primary Ipilimumab + IMO-2125 Efficacy Evaluable (PIIEE) Population: all patients who are ipilimumab-naïve on study entry (including those who received ipilimumab only in the adjuvant setting) and who are treated at the RP2D for the IMO-2125 + ipilimumab combination, regardless of which phase of the study they receive it; and who received at least one dose of each study drug.
- Secondary Ipilimumab + IMO-2125 Efficacy Evaluable (SIIIE) Population: all patients who are not ipilimumab-naïve on study entry and who are treated at the RP2D for the IMO-2125 + ipilimumab combination, regardless of which phase of the study they receive it; and who received at least one dose of each study drug.
- Primary Pembrolizumab + IMO-2125 Efficacy Evaluable (PPIEE) Population: all patients who are treated at the RP2D for the IMO-2125 + pembrolizumab combination, regardless of which phase of the study they receive it; and who received at least one dose of each study drug.

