ICH	International Council for Harmonisation
IMO	Immune Modulatory Oligonucleotide
irAE	Immune-related adverse event
irRC	Immune-related response criteria
irRECIST	Immune-related reponse evaluation criteria solid tumors
ISR	Injection site reaction
LFT	Liver function test
MLE	Maximum Least-square Estimation
MTD	Maximum tolerated dose
NCI	National Cancer Institute
ORR	Objective response rate
OS	Overall survival
PD	Progressive disease
PFS	Progression-free survival
PI	Principal Investigator
PK	Pharmacokinetic
PR	Partial response
Pr	Probability
PRO	Patient reported outcome
PT	Prothrombin time
RBC	Red blood cell
RP2D	Recommended Phase 2 dose

SAE	Serious adverse event
SD	Stable disease
ULN	Upper limit of normal
WBC	White blood cell

DEFINITIONS

Adverse Event	An adverse event (AE) is any reaction, side effect, or other untoward event, regardless of relationship to study drug, which occurs anytime during the study.
DLT Evaluable Population	All subjects in the Safety Population who continue participation in the study for the entire DLT evaluation period, or who discontinue prematurely due to a DLT.
DLT Evaluation Period	The DLT evaluation period will be Cycle 1 (Weeks 1 through 4).
Safety Population	All subjects who received at least one dose of IMO-2125.
Serious AE	An AE occurring at any dose that: results in death; is a life-threatening experience; requires hospitalization or prolongation of an existing hospitalization; results in a persistent or significant disability/incapacity; or is a congenital anomaly/birth defect in the offspring of a subject who received study drug; or important medical event that, although not immediately life-threatening, requires intervention in order to prevent one of the listed serious outcomes listed.
Study Drug	IMO-2125 in combination with ipilimumab or pembrolizumab
Treatment-emergent AE	AEs with an onset date on or after the date of the initial dose of study drug, or an AE that worsens after the date of the initial dose of study drug.

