3. STUDY DESIGN AND PLAN

3.1 Overview

This is a two arm open-label Phase 1/2 study to assess the safety, tolerability, PK, immunogenicity, and efficacy of IMO-2125 when administered in combination with ipilimumab or in combination with pembrolizumab. Subjects with metastatic melanoma who have experienced symptomatic or confirmed radiographic progression to their most recent treatment regimen (anti-PD-[L]1 alone or in combination) will be eligible. Prior BRAF or MEK inhibitor treatment is not required. The study will be conducted in two parts: a dose-escalation portion (Phase 1) to evaluate safety and tolerability of multiple dose levels and a Phase 2 portion to assess preliminary efficacy.

3.1.1 Phase 1

The Phase 1 portion of the study is will explore escalating dose levels of IMO-2125 (from 4 to 32 mg with de-escalation to 2 mg allowed for each IMO-2125 combination). For each cohort, IMO-2125 will be administered as a once-weekly intratumorally injection for 3 consecutive weeks in Cycle 1, followed by intratumorally injections on Weeks 5, 8, 11, 17, 23, and 29 (Day 1 of Cycles 2 through 7). Both ipilimumab and pembrolizumab will be administered as per the USPI every 3 weeks beginning Day 1 of Week 2. Continued dosing of pembrolizumab following the study treatment period is permitted at the discretion of the Investigator for subjects in the IMO-2125 + pembrolizumab treatment arm. The dosing schedule is summarized in Table 1.

Table 1: Schedule of Dosing for Phase 1 and Phase 2

	Cycle															
	1				2			3			4			5	6	7
Study week	1	2	3	4	5	6	7	8	9	10	11	12	13	17	23	29
IMO-2125 + ipilimumab																
IMO-2125	X	X	X	-	X	-	-	X	-	-	X	-	-	X	X	X
Ipilimumab	-	X	-	-	X	-	-	X	-	-	X	-	-	-	-	-
IMO-2125 + pembrolizumab																
IMO-2125	X	X	X	-	X	-	-	X	-	-	X	-	-	X	X	X
Pembrolizumab	-	X	-	-	X	-	-	X	-	-	X	X ¹				

Note: On weeks when the combinations are administered, administration of ipilimumab or pembrolizumab will be first, followed by IMO-2125. IMO-2125 administration must occur within a ±2 day window of the scheduled dosing day.

¹ For subjects in the IMO-2125 + pembrolizumab treatment arm, continued pembrolizumab dosing per the approved product label is permitted at the discretion of the Investigator

Subjects assigned to 11 weeks of IMO-2125 under previous versions of the protocol who have not yet reached the end of the Treatment Period may receive the Week 17, 23, and 29 injections at the discretion of the treating Investigator.

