Each cohort will be monitored for the occurrence of DLTs. The DLT evaluation period will be Cycle 1 (Weeks 1 through 4). If a subject discontinues study participation before the DLT evaluation period is finished due to reasons other than experiencing a DLT, that subject must be replaced so that the cohort may be properly evaluated. More information about the review of DLTs and the escalation of dose levels between cohorts is provided in Section 3.1.3, Section 3.1.4, and Section 3.1.5.

There are 3 subjects planned per cohort. During Phase 1, the sponsor will assign subjects to a treatment arm (IMO-2125 + ipilimumab or IMO-2125 + pembrolizumab) by cohort.

After completing the DLT evaluations for all planned IMO-2125 doses in either combination, supplemental cohorts of up to 5 subjects each may be enrolled with either combination at doses up to and including the MTD. After completion of either Phase 1 treatment arm and determination of the RP2D for that arm, the Phase 2 portion for the

completed treatment arm may be initiated. It is not necessary for Phase 1 to be completed in both treatment arms before Phase 2 is started.

3.1.2 Phase 2

The Phase 2 portion of the study will assess preliminary efficacy, using investigator-assessed RECIST v1.1, of IMO-2125 + ipilimumab, IMO-2125 + pembrolizumab, and any additional combinations that are studied in Phase 1. The dose level of IMO-2125 to be administered for each treatment arm will be the RP2D for the combination, as determined in Phase 1. Phase 2 will enroll up to 60 subjects treated at the IMO-2125 + ipilimumab RP2D. This will include at least 21 subjects in the primary IMO-2125 + ipilimumab efficacy-evaluable population and up to 20 subjects in the secondary IMO-2125 + ipilimumab efficacy-evaluable population. In the IMO-2125 + pembrolizumab Phase 2 cohort, enrollment will continue until 21 subjects in the IMO-2125 + pembrolizumab efficacy-evaluable population have been treated at the IMO-2125 + pembrolizumab RP2D. Phase 1 subjects treated at the RP2D for either combination may contribute to these totals. A two-stage design will be used to test for clinically and statistically relevant clinical activity. A treatment arm will stop if an interim futility analysis shows there is insufficient evidence of a clinically relevant response rate after 10 subjects (Stage 1).

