- Isolated, asymptomatic elevations in biochemistry laboratory values lasting \leq 14 days. This includes electrolyte abnormalities that respond to medical intervention.

Ipilimumab-related DLTs:

- Grade \geq 4 immune-mediated dermatitis (except skin reaction at site of injection);
- Grade \geq 3 immune-mediated endocrinopathy (with the exception of Grade 3 autoimmune thyroiditis that resolves to Grade 1 or baseline within 28 days of onset);
- Grade \geq 3 immune-mediated enterocolitis;

- Grade ≥ 3 immune-mediated hepatitis with the exception of Grade 3 immune-mediated hepatitis that resolves to Grade 1 or baseline within 28 days of onset;
- Grade ≥ 3 immune-mediated neuropathy, pancreatitis, meningitis, nephritis, and pneumonitis that are considered to be possibly, probably, or definitely related to study therapy as determined by the Investigator;
- Any persistent IMO-2125-related toxicity that leads to a delay of scheduled (per standard of care) ipilimumab > 14 days.

Pembrolizumab-related DLTs:

- Grade ≥ 3 pneumonitis or recurrent Grade 2 pneumonitis;
- Grade ≥ 3 nephritis;
- Grade ≥ 3 infusion-related reactions;
- Inability to reduce corticosteroid dose to 10 mg or less of prednisone or equivalent per day within 12 weeks;
- Any Grade ≥ 3 treatment-related AE that recurs.

If at any time during the study, a subject experiences a DLT as outlined above, the toxicity in question must be assessed for attribution based on the known toxicity profiles for ipilimumab, pembrolizumab, and IMO-2125. If assessment can be clearly attributed to one of the drugs in the combination, then dosing should be interrupted and the toxicity should be followed until resolution, stabilization, or return to baseline. Treatment with the other agent may continue during this time period. If attribution cannot be clearly ascribed to one agent versus the other, then both IMO-2125 and ipilimumab (or pembrolizumab) should be stopped and the toxicity should be followed until resolution, stabilization, or return to baseline. If treatment is to be resumed, then re-initiation criteria must be met. If the DLT was clearly related to IMO-2125 or if attribution cannot be clearly determined, then IMO-2125 must be administered at a lower dose level (a minimum reduction of at least 1 dose level). If the DLT recurs after a dose level reduction, then treatment should be discontinued.

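### The DLT Evaluable Population counts a subject who never received the checkpoint inhibitor as DLT-free, and drops and replaces a subject with a Cycle 1 DLT who then leaves the study for another reason

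*SAP*

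**What the plan says.** The SAP defines the DLT Evaluable Population in the Definitions table and again, in matching terms, in Section 6. It consists of Safety Population subjects "who continue participation in the study for the entire DLT evaluation period, or who discontinue prematurely due to a DLT". According to Section 6 this set "will be used only for Cohort Review Committee meetings to determine if the dose may be escalated".

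The surrounding rules are:

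- **Entry condition (Section 6):** "Safety Population: all patients who received at least one dose of IMO-2125". No dose of the second agent is needed.
- **Timing (Section 3.1.1):** "Both ipilimumab and pembrolizumab will be administered as per the USPI every 3 weeks beginning Day 1 of Week 2". The DLT evaluation period is Cycle 1, Weeks 1 to 4.
- **Replacement (Section 3.1.1):** the rule begins "If a subject discontinues study participation before the DLT evaluation period is finished due to reasons other than experiencing a DLT, that subject must be", and the action it requires is replacement. There is no exception for a subject who has already had a DLT.
- **Consequence of a DLT clearly attributed to one drug (Section 3.1.5):** "then dosing should be interrupted and the toxicity should be followed until resolution, stabilization, or return to baseline". The other agent may continue.
- **Study participation (Section 3.2.2):** subjects who stop treatment before progression stay in follow-up. After progression they move to telephone survival follow-up. A subject completes the study only at death or study end.
- **MTD rule (Section 3.1.3):** beta(1,1) prior for the DLT rate at each dose level. A level is admissible if the posterior probability that the rate exceeds 0.25 is below 0.80. No analysis population is named.

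The three efficacy populations in Section 6 do require a dose of both agents.

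**The concern.** Phase 1 is meant to characterise the safety of IMO-2125 given with a checkpoint inhibitor, but evaluability is defined by presence in the study and not by exposure to the combination. Two errors follow, both in the direction of escalation.

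1. **An unexposed subject counts as tolerating the combination.** A subject who receives IMO-2125 in Week 1, gets no ipilimumab or pembrolizumab in Cycle 1 and stays in the study enters the denominator as DLT-free.
2. **An observed DLT can leave the count.** A DLT interrupts dosing; it does not in itself end study participation. A subject with a Week 2 DLT who withdraws consent in Week 3 for an unrelated reason has neither stayed for the whole period nor discontinued because of the DLT. That subject falls outside the set and must be replaced.

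With 3 planned subjects per cohort, a single misclassification can change the apparent result at a dose level.

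**Working it through.** **Nearest figure in the plan.** The population definition carries no number. The closest one is Table 3 (Phase 2 DLT boundaries, prior beta(0.6, 1.4), stop if Pr(rate > 0.25 | data) > 0.80). For x DLTs, take the largest n for which the upper tail of Beta(0.6 + x, 1.4 + n − x) above 0.25 exceeds 0.80. For x = 3 to 10 this gives 7, 10, 13, 17, 20, 24, 27, 31. Table 3 prints 7, 10, 13, 17, 20, 24, 27, 29. Seven of eight entries agree, so the posterior method is reproduced. The last entry has no bearing on this point.

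**Phase 1 rule.** With a beta(1,1) prior and x DLTs in n subjects, the posterior is Beta(1 + x, 1 + n − x). Its tail above 0.25 equals P(Binomial(n + 1, 0.25) ≤ x).

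| DLTs / subjects | Calculation | Pr(rate > 0.25) | Against 0.80 |
|---|---|---|---|
| 0/3 | 0.75^4 | 0.316 | passes |
| 1/3 | 0.3164 + 0.4219 | 0.738 | passes |
| 2/3 | 0.3164 + 0.4219 + 0.2109 | 0.949 | fails |
| 2/4 | 0.2373 + 0.3955 + 0.2637 | 0.896 | fails |

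**Gap 2, the dropped DLT.** Two of three subjects have a DLT, and one of those two withdraws consent before the end of Week 4.

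- As written, that subject is excluded and replaced. With a DLT-free replacement the count is 1/3, giving 0.738: passes.
- With the DLT kept and no replacement, the count is 2/3, giving 0.949: fails.
- With the DLT kept and the DLT-free replacement also counted, it is 2/4, giving 0.896: fails.

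**Gap 1, the unexposed subject.** Two exposed subjects show 1 DLT, and the third never received the checkpoint inhibitor.

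- As written, the count is 1/3, giving 0.738: passes.
- With the unexposed subject replaced, the completed cohort is 1/3 (0.738, passes) or 2/3 (0.949, fails), depending on the replacement.

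The cost is therefore best put as a probability. From the table, a cohort of 3 passes if it shows at most 1 DLT. Let p be the true DLT rate, with independent subjects. The SAP gives no true rate, so a range is assumed.

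- Three exposed subjects: P(at most 1 DLT) = (1 − p)^3 + 3p(1 − p)^2.
- Two exposed and one scored as DLT-free: P(at most 1 DLT) = 1 − p^2.

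| Assumed p | Three exposed | Two exposed, one scored DLT-free |
|---|---|---|
| 25% | 0.844 | 0.938 |
| 40% | 0.648 | 0.840 |
| 50% | 0.500 | 0.750 |

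**The case against.** Several points on the other side limit the finding.

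- **Progression.** A reader might infer that a DLT subject who progresses in Week 3 is also dropped. Section 3.2.2 does not support this: progression moves a subject to survival follow-up and does not end participation. That subject remains evaluable and is not replaced. The gap is confined to withdrawal of consent and similar departures within four weeks.
- **Ipilimumab delays.** Section 3.1.5 makes a delay of ipilimumab beyond 14 days a DLT when persistent IMO-2125-related toxicity causes it. Those subjects are counted. Other reasons for a missed dose are not covered, and the pembrolizumab list has no matching item.
- **The incomplete cohort.** It is tempting to set 1/3 (0.738) against 1/2 (0.844) and say that the unexposed subject alone turns a failing dose into a passing one. A cohort left at two is not the proper comparison, because the unexposed subject would be replaced under a corrected rule.
- **Committee oversight.** The Cohort Review Committee (CRC) reviews all safety data and decides whether DLTs occurred (Section 3.1.4), and later toxicity informs the RP2D (Section 3.1.5). A dropped DLT stays visible in the Safety Population. This softens the problem, but nothing in the SAP returns the subject to the evaluable set.
- **Other documents.** The CRC charter and the protocol are not at hand and may be tighter. The SAP definition nevertheless reads as complete, appears twice and defers to neither for evaluability.

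**Conclusion.** Both gaps follow from the literal wording of the Definitions table and Sections 3.1.1 and 6, and both bias the escalation count downward. Losing one of two DLTs can move a dose level from 0.949 (or 0.896) to 0.738, across the 0.80 limit. Scoring one unexposed subject of three as DLT-free adds 0.094, 0.192 and 0.250 to the chance of at most 1 DLT at assumed true rates of 25%, 40% and 50% (0.938 − 0.844, 0.840 − 0.648, 0.750 − 0.500).

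The comparisons with 0.80 assume that the MTD posterior of Section 3.1.3 uses this population. Section 6 ties the set to CRC escalation decisions only, and Section 3.1.3 names no denominator. The probabilities for the unexposed subject also assume that this subject is certain to be scored without a DLT, although an IMO-2125-only DLT remains possible.

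A reader might infer that such DLTs vanish from the trial. The documents do not support that: what is lost is membership of the evaluable set, not the committee's sight of the event.

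**What to change.** Redefine the DLT Evaluable Population, in the Definitions table and Section 6, as treated subjects who meet either condition:

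- (a) a DLT in Cycle 1, whatever the later reason for leaving; or
- (b) no DLT, completion of Week 4, and exposure in Cycle 1 to both agents (one dose or more of each, the standard already set for the efficacy populations). Any further minimum exposure is for the sponsor to set.

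Limit replacement in Section 3.1.1 to subjects who meet neither (a) nor (b). State in Section 3.1.3 that the MTD posterior is computed on this set, and extend the statement of use in Section 6 to match. Check the CRC charter for the same wording.

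The cost is a few sentences of text and an occasional extra replacement subject in a 3-subject cohort.
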